### Inclusion Criteria:

- Women who present with symptoms of OAB, defined as a condition characterized by urgency, with or without urgency incontinence, usually with frequency and nocturia in the absence of obvious pathology or infection [9], with atrophic vaginitis.
- Postmenopausal:
  - by history, defined as twelve months or greater since last menstrual period
  - surgical menopause with removal of bilateral ovaries
  - age over 55 if they have had a previous hysterectomy alone without removal of bilateral ovaries.
- English language skills sufficient to complete questionnaires
- Clinical indication for vaginal estrogen use (hypoestrogenic findings on physical examination)
- Patients not currently receiving vaginal estrogen therapy

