### ***Patient Data Collection:***

**Visit 1 (baseline):** After enrollment and informed consent is obtained, patients will be asked to complete the OAB-q, a validated questionnaire, (**Appendix 3**) to measure OAB-related symptoms and quality of life [17]. Voided urines will be collected in a hat for 16SrRNA, PCR and protein analysis. A perineal swab will then be collected and assessed by 16S rRNA sequencing. Then a 30 mL vaginal lavage will be collected from the anterior wall of the vagina using sterile water for PCR and protein analysis. A vaginal swab will also be collected from the posterior fornix prior to the catheterized urine collection and assessed by 16S rRNA sequencing. Following the collection of the vaginal swab, a post void residual specimen will be collected by transurethral catheter, which is part of our standard practice for new patients. This specimen will be sent for standard clinical microbiology culture, EQUC and 16S rRNA gene evaluation. The specimens destined for the [name] lab will be stored on ice until pick up and transport. The swabs and urine for culture will be stored at room temperature until processed. The urine for sequencing will be refrigerated.

Demographic information and clinical characteristics will be collected, including age, parity, medical illness, previous hysterectomy, previous incontinence surgery, post void residual volume and body mass index (**Appendix 4**).

Physical examination will be completed, including evaluation for pelvic organ prolapse with the POP-q examination, which is part of a standard initial clinical evaluation.

Patients will be counseled on the evidence-based, first-line options for the treatment of OAB, including behavioral modifications, physical therapy, and vaginal estrogen per standard practice in our clinic. All study participants will be provided vaginal estrogen Premarin Cream® 0.625 mg conjugated estrogen/gram and instructed to use 0.5 grams twice weekly with the applicator. This is based on the clinical practice guidelines for vaginal estrogen use in postmenopausal women with urogynecological complaints developed by the Society of Gynecological Surgeons Systematic Review Group [18]. Patients will receive compensation at visit one with a parking voucher.

Patients will be given a medication diary for the use of vaginal estrogen to assess compliance (**Appendix 5**).

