**Visit 2 (12 weeks):** Patients will be scheduled to return at twelve weeks from the initial visit for follow up which is part of our standard practice. They will be called a few days prior to the scheduled appointment as a reminder of the appointment and reminder to bring the medication diary. At the follow up, patients will repeat the OAB-q to reassess symptoms and quality of life measures. Again, voided and transurethral catheterized urine samples will be collected for analysis as described in visit 1. The perineal swab, vaginal lavage sample, and vaginal swab samples will also be collected at this visit and processed as described in visit 1. The patient will be screened for vaginal bleeding or spotting. The patient will be compensated with a second parking voucher at the conclusion of the study participation.

At this point, based on the patients' response to treatment, they may continue using vaginal estrogen. The symptoms of OAB will be reassessed and the next step in treatment will be based on the clinician's usual practice.

**Adverse Event Reporting:** We do not anticipate adverse events with this protocol; however as with all clinical protocols, it is feasible that a variety of unforeseen adverse events could occur. The risk of serious adverse event from the study participation in this protocol is extremely low and could include allergic reaction to the estrogen preparations, which would be considered reportable.

We would also report privacy breaches. There is also an unlikely risk of privacy violation despite diligent adherence to protection of all identified human data, using the Loyola secure server and in compliance with our institutional policies.

**Sample Collection and Preparation:** Consenting participants will contribute 2 catheterized urine samples and two voided urine samples: at the first visit and 12 weeks later. Urine samples obtained at the first visit are part of routine standard care and thus will be sent to the Clinical Microbiology Lab for standard urine culture. The Clinical Microbiology Lab also will assess the catheterized urine sample by EQUC. The Genomics Facility will perform 16S rRNA gene sequencing on the voided and catheterized urine samples and the [name] lab will do PCR and protein analysis. Both urine samples obtained at 12 weeks will be assessed by 16S rRNA gene sequencing, PCR and protein analysis. Catheterized urine samples will also be assessed by EQUC.

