### **Ethics and Patient Consent**

Patients will be identified when they present to the Loyola Urogynecology outpatient clinic for management of their OAB symptoms. Co-investigators ([name], [name]) will identify and recruit patients for participation. The consent form will be read to the patient; it will describe the nature of the trial and potential associated risks and benefits. Potential participants will be informed that neither participation nor refusal will influence the care received at Loyola University Medical Center. A copy of the consent form will be given to them. Participation is completely voluntary and they may discontinue participation in the study at any time

**Patient Compensation:** Patients will receive a three months' supply of Premarin vaginal cream at no cost. Patients will receive a five dollar parking voucher at both visit one and two for their participation in the study.

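### The time from last cream application to week-12 sampling is neither fixed nor modelled, so a residual-cream artefact cannot be excluded, chiefly in the vaginal, perineal and voided specimens

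*Combined protocol and SAP*

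**What the plan says.** **Exposure.** Under Patient Data Collection, Visit 1 (baseline), women are given the cream and "instructed to use 0.5 grams twice weekly with the applicator". No days, spacing or time of day are stated. Inclusion Criteria require "Patients not currently receiving vaginal estrogen therapy", and Recruitment places the baseline measurements before treatment. Ethics and Patient Consent adds "Patients will receive a three months' supply of Premarin vaginal cream at no cost", so use can run up to visit 2.

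**Sampling.** Visit 1 lists voided urine, a perineal swab, a 30 mL lavage of the anterior vaginal wall, a posterior-fornix swab and then catheterized urine. For visit 2 the plan says "Patients will be scheduled to return at twelve weeks from the initial visit for follow up". The call beforehand serves "as a reminder of the appointment and reminder to bring the medication diary". At the visit, "The perineal swab, vaginal lavage sample, and vaginal swab samples will also be collected at this visit and processed as described in visit 1". For urine the text is "Again, voided and transurethral catheterized urine samples will be collected for analysis as described in visit 1".

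**Control and analysis.** Recruitment makes each woman her own control, and there is no second arm. Under Sequencing, the negative control is an extraction blank without urine. The Statistical Analysis Plan models each diversity measure on time, OAB-q symptom severity, physical therapy, weeks of estrogen compliance and body mass index, with random intercepts. Time since last application is not listed. A diary is issued to assess compliance; its form (Appendix 5) is not in the text available for review.

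**The concern.** The product is placed where two of the specimens are taken and close to where two others are taken. Baseline samples precede any study cream, while week-12 samples come from women who may have applied it the night before or several days earlier. In a single-arm design, anything specific to the second visit goes into the change from baseline, and for diversity that means the time coefficient. If residue affected sequencing, PCR or protein results, the analysis could not tell that from a response to estrogen. The before-after comparison of diversity and antimicrobial peptide (AMP) levels is the purpose of Aim 1. An interval that varies between women would also add noise to the change scores used in the planned Spearman correlations.

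**Working it through.** The plan states no figure on this point. Its one design figure, power 0.816 with 60 women, does not bear on it.

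**1. Share of women sampled soon after an application**

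Input from the plan: two applications per 7 days. Assumptions: full adherence, use continuing to visit 2, and visit time unrelated to application days. For gaps g1 + g2 = 7 days, the share sampled within t days of an application is [min(t, g1) + min(t, g2)] / 7.

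| Spacing (assumed) | within 24 h | within 48 h | within 72 h |
|---|---|---|---|
| 3 and 4 days | (1+1)/7 = 29% | (2+2)/7 = 57% | (3+3)/7 = 86% |
| consecutive days (1 and 6) | (1+1)/7 = 29% | (1+2)/7 = 43% | (1+3)/7 = 57% |

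With 3/4-day spacing, the mean time since last application is (3²/2 + 4²/2)/7 = 12.5/7 = 1.8 days, with a maximum of 4 days. With consecutive-day use the maximum is 6 days. For study cream, the share at baseline is 0%.

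**2. Which specimens are exposed**

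- Vaginal swab and lavage: taken in the area of application.
- Perineal swab and voided urine: taken near it or passing it.
- Catheterized urine: drawn through the urethra from the bladder. This is the EQUC specimen, so direct carry-over is much less plausible.

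**3. Dilution of the lavage**

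Take 0.5 g and 30 mL from Visit 1 and assume about 1 g/mL. Even a whole dose left in place would be 0.5/30.5 = 1.6% of the volume. Bioinformatics Analysis names the Shannon and inverse Simpson indices, which depend on relative abundances, so an inert diluent would not in itself move them. What remains possible is assay inhibition or added material, on which the documents are silent.

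**4. Illustration of consequence (artefact size assumed)**

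Suppose estrogen has no effect, and a share f of women carry an artefact of a standard deviations of the change score. The mean change is f·a, its standard deviation is √(1 + f(1−f)a²), and the noncentrality of a paired t test is √n times their ratio. For n = 20, a = 0.5 and f = 4/7: mean 0.286, SD 1.030, noncentrality 1.24, and rejection at two-sided 0.05 in 22%. The ranges below run from f = 2/7 to f = 4/7.

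| Assumed artefact | n = 20 | n = 60 |
|---|---|---|
| 0.25 SD | 6–9% | 8–19% |
| 0.5 SD | 9–22% | 19–56% |
| 1.0 SD | 20–59% | 51–97% |

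The nominal rate is 5%. The table shows only that a moderate artefact would matter if there were one.

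**5. Cost of handling it by exclusion**

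Aim 1 gives a pilot of 20, and Possible Limitations gives about 7% loss: 20 × 0.93 = 18.6, or about 19 women. Excluding those sampled within 24 hours removes 19 × 2/7 = 5.4, or about 5.

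**The case against.** A reader might infer that residual cream is present in the week-12 specimens and will be reported as an estrogen effect. The documents do not support that. They say nothing on how long cream persists or whether it interferes with any assay, and the shares above count time since application only. This objection stands, and it limits the point to an artefact that cannot be excluded.

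A reader might also extend the point to the urinary microbiome, on which the main hypothesis and the species-count prediction under Expectations rest. That prediction uses EQUC on catheterized urine, the specimen least exposed. This too stands. The dilution route is weak on the plan's own quantities.

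Two further objections stand in part. Sampling across the cycle could be defended as estimating an average on-treatment state, since the stated contrast is simply before versus following 12 weeks of treatment. But the plan does not choose that target, and it does not ensure that sampling is spread over the cycle. Second, the diary may already hold application dates; without Appendix 5 their absence cannot be claimed. Even so, the plan's stated use of the diary is compliance, and the model takes only weeks of compliance.

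Finally, the lack of a comparator is a larger, separate limitation that this point does not resolve. Nor is the before-and-after asymmetry strict for vaginal estrogen in general, because no washout is stated for earlier products. It holds for the study cream.

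**Conclusion.** The point holds as a cheap improvement to the conduct of visit 2. The interval from last application to week-12 sampling is neither fixed nor in the model, and no vehicle arm or cream blank would reveal a residue effect. An artefact cannot be excluded for the vaginal swab and lavage, nor, with less force, for the perineal swab and voided urine. For catheterized urine and EQUC it is much less plausible.

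The exposure shares of about 29% within 24 hours and 43% to 57% within 48 hours rest on full adherence, use up to visit 2, visits unrelated to application days, and the two spacings considered. The size and direction of any artefact are unknown. No sample-size or power figure changes.

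**What to change.** Leave the regimen as it is.

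- Schedule visit 2 at a common point in each woman's own application cycle, fitting the appointment to her days and not the reverse.
- Confirm this in the reminder call already planned.
- Record the date and time of the last application at visit 2, from the diary if it holds them.
- As a sensitivity analysis, examine the vaginal, perineal and voided-urine results by time since last application. This is preferable to relying on exclusion, which could cost about 5 of 19 women in the pilot if timing were left uncontrolled and would remove almost none if it were controlled.

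The cost is a line in the visit schedule, a question in an existing call, one recorded item and one extra analysis. The downsides are less freedom in choosing appointment days and low precision of the sensitivity analysis in a small pilot; once timing is controlled, the narrow spread of intervals makes it mainly a check on departures. A common sampling point removes the variation between women but does not test whether cream disturbs an assay. A cream-spiked blank run through the assays would do so, as an optional addition at some laboratory cost.

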Immediately after collection, the human subjects-certified research team personnel will refrigerate and de-identify each urine sample, removing all protected health information prior to submission to any non-clinical investigators. Only the study ID will be available to individuals who are not involved in human subject recruitment, retention and oversight. Within 4 hrs, 1 aliquot of the catheterized urine sample will be sent to the clinical microbiology lab for standard culture and EQUC. A 2nd aliquot of the voided and catheterized urine sample will be sent to the genomics facility, where it will be inventoried and maintained in 10% DNA preservative (e.g., AssayAssure) at -80°C until bacterial DNA isolation and sequence analysis. After these analyses, leftover samples will remain stored in this biorepository for potential future IRB-approved analyses. A 3rd set of samples will be sent to the [name] lab for analysis of candidate AMPs (e.g. RNase 7, cathelicidin,  $\beta$ -defensins, s100A7) in urinary, vaginal and perineal epithelial cells (obtained from urine and vaginal lavage) and perineal/vaginal swabs.

**Sequencing:** Genomic DNA (gDNA) will be extracted from urine with the Qiagen DNeasy Blood and Tissue kit as described previously. We will amplify the V4 region of 16S rRNA, add Illumina sequencing adapters and dual-index barcodes, purify the resulting amplicons, quantify, and sequence using the Illumina MiSeq System. To assess potential DNA contamination, an extraction (no urine) negative control will be processed with the samples and sequenced in every run. To ensure reproducibility, each sample will be independently extracted and sequenced at least twice. This is the protocol used for our recent publications [1, 2].

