**Bioinformatics Analysis:** Quality control and de-multiplexing of sequence data are done with onboard MiSeq Control software and MiSeq Reporter (current version: 2.1.43). The *mothur* pipeline, specifically formatted for its use with MiSeq-generated data will combine paired end reads and remove contigs of incorrect length (<285 bp, >300 bp), contigs containing ambiguous bases and chimeric sequences. Within *mothur*, sequences will be assigned to OTUs and taxonomically classified using a naïve Bayesian classifier and the *mothur*-customized RDP training set v9. Alpha diversity metrics (inverse Simpson index, Shannon index), beta diversity metrics (PCoA plots), mean sequence abundance, and dendrograms will be generated using *mothur*, METAGENassist and R. This protocol was used for our recent publications [1, 2].

**Standard and Expanded Urinary Quantitative Culture (EQUC) Procedures:** Catheterized urine samples are processed with standard and/or EQUC methods. Standard urine culture involves inoculation of 0.001 mL of urine onto 5% sheep blood agar plate (BAP) and MacConkey agar plate, incubated aerobically at 35°C for 24h. Thus, the level of detection for standard culture is 10^3 CFU/mL, represented by 1 colony of growth on either plate. In contrast, EQUC involves inoculation of 100X (0.1mL) more urine onto diverse types of media (BAP, chocolate agar, colistin and nalidixic acid (CNA) agar, CDC anaerobe 5% BAP) with incubation in more environments and temperatures (5% CO2 at 35°C for 48 h, aerobic conditions at 35°C & 30°C for 48 h, Campy gas mixture (5% O2, 10% CO2, 85% N) or anaerobic conditions at 35°C for 48 h). The level of detection for EQUC is 10 CFU/mL, represented by 1 colony of growth on any plate. Each morphologically distinct colony type in both standard and EQUC procedures will be counted and isolated on a different plate of the same media to prepare a pure culture to be used for identification with Matrix-Assisted Laser Desorption/Ionization Time-of Flight (MALDI-TOF) mass spectroscopy. This is the protocol used for our recent publications [1, 2].

**Biolog Assay:** Characterization of bacterial strains isolated from urine obtained from the female bladder by transurethral catheter will facilitate our understanding of the role that these bacteria play in the bladder. For

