example, commensal bacteria of the gut are known to inhibit the growth of pathogenic bacteria by outcompeting the pathogen for available nutrients, a process called colonization resistance.

The Biolog assay is de rigeur for determining bacterial growth characteristics. It requires a device that the Loyola team does not possess, but Kimberly-Clark does. Thus, the isolates will be sent to Kimberly-Clark for Biolog characterization.

The urinary bacterial isolates received by Kimberly-Clark will be undergo phenotypic analysis of their growth curves and biochemical utilization profiles. To determine growth rates isolates will be grown in a nutrient rich broth and a nutrient limited broth. Bacterial growth will be measured kinetically using a spectrophotometer under the appropriate atmospheric conditions. Biochemical utilization profiles of the isolates will be determined using a series of Biolog plates, either endpoint or kinetic growth will be measured.

**Data Storage and Confidentiality:** Following HIPPA guidelines, patient identifiable data will be coded to protect each patient's identity. The data obtained from the patients will be entered onto electronic forms in the secure Redcap database. We are familiar with using this technology from other studies. It is efficient to complete in a clinical setting and minimizes data entry errors. The data will be presented in peer reviewed manuscripts and other public presentations at the group level only. No individual patients will be identified.

**Statistical Analysis Plan:** All data will be maintained on the Loyola secure, HIPAA-compliant research server. Only human-subjects certified team members will have access to identified data. Laboratory assessment will be performed using anonymized data and unique study numbers for each subject.

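### Samples are coded by subject and no section masks the culture reader to visit, so masking of the before-after EQUC species count is not assured

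*Combined protocol and SAP*

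**What the plan says.** On coding, the Statistical Analysis Plan states: "Laboratory assessment will be performed using anonymized data and unique study numbers for each subject". Sample Collection and Preparation has staff de-identify each urine, "removing all protected health information prior to submission to any non-clinical investigators", and adds: "Only the study ID will be available to individuals who are not involved in human subject recruitment, retention and oversight". These are privacy provisions. None mentions visit, a specimen-level code, reading order or access to earlier results.

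On timing: "Consenting participants will contribute 2 catheterized urine samples and two voided urine samples: at the first visit and 12 weeks later". For culture: "Within 4 hrs, 1 aliquot of the catheterized urine sample will be sent to the clinical microbiology lab for standard culture and EQUC". Each urine is therefore cultured as it arrives, and a woman's two specimens are not stored and read together.

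On the reading itself, the section on standard and EQUC procedures says: "Each morphologically distinct colony type in both standard and EQUC procedures will be counted and isolated". The resulting pure cultures are then identified by MALDI-TOF.

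On design, Recruitment makes each woman her own control. Expectations predicts an average of about 3 EQUC species before estrogen, moving towards 1 afterwards.

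**The concern.** With no concurrent group, visit is the treatment contrast. Anything that makes the laboratory treat week-12 plates differently from baseline plates goes straight into the estimated change. The EQUC count is open to this because its first step is a human judgement about which colonies differ, made in a study whose expected direction is written down in advance.

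The two kinds of picking error are not equally harmful. If a reader splits one species into several colony types, identification merges them again. If a reader passes over a colony type, it is never identified, and the count falls by one unless the same species is picked from another plate. Less thorough picking at week 12, or more thorough picking at baseline, would push the count in the hypothesised direction. This cannot be undone once the plates are read. De-identification protects the patient but does not protect this comparison.

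**Working it through.** The plan gives no figure on masking or reader agreement, so there is nothing of its own to reproduce on this point. Its one design figure is power of 0.816 at 60 subjects by the Wilcoxon-Mann-Whitney test. That can be neither confirmed nor refuted, because the group split, sidedness and full distributions are not stated, and this point does not depend on it.

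**Step 1. Is masking to visit stated anywhere?** The sections from Methodology to Possible Limitations were read for it. The only identifier described is per subject. No section says that EQUC readers are masked, that specimens have their own codes, or that reading order is randomised.

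**Step 2. Could a reader place a specimen in time?** A shared number links two specimens but does not order them. Order would have to come from arrival date or earlier records. Culture on arrival, 12 weeks apart, under a recurring number makes that plausible. It remains an inference, since the label content and what the reader sees are not described.

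**Step 3. Illustrative size.** Inputs: a largest anticipated fall of 3 − 1 = 2 species (Expectations), and an assumed visit-dependent shift of 0.2 to 0.5 colony types per woman. If every missed colony type costs one species, which is an upper bound because the species may be picked elsewhere:

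- share of a 2-species fall: 0.2/2 = 10% to 0.5/2 = 25%;
- share of a 1-species fall (assumed, since Expectations anticipates a smaller difference than in the earlier study): 0.2/1 = 20% to 0.5/1 = 50%.

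**Step 4. Sensitivity of the false-positive rate.** Assumptions: no true effect, bias *b* all in one direction, SD of the paired change 2 to 4 species, and a two-sided 5% paired test by normal approximation. The rejection probability is Φ(*b*√n/SD − 1.96) + Φ(−*b*√n/SD − 1.96). Both sample sizes in the protocol are used (20 and 60).

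| *b* (species) | n = 20 | n = 60 |
|---|---|---|
| 0.25 | 6% to 9% | 8% to 16% |
| 0.5 | 9% to 20% | 16% to 49% |

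For example, with *b* = 0.5, n = 20 and SD = 2: 0.5 × √20/2 = 1.118, and Φ(−0.842) + Φ(−3.078) = 0.201. The lower end of each range is SD = 4. The planned mixed model would not give exactly these values. They show sensitivity and are not evidence that bias exists.

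**The case against.** A reader might infer that the laboratory receives both specimens under an identical label, that the culture reader can tell the visits apart, and that the count is unblinded. The documents do not support that. They are silent on label content, on any specimen suffix, and on whether dates or earlier results are visible. A reader would have to recall or look up a number seen 12 weeks before. Nor does any section say that the culture readers know the hypothesis.

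It is also tempting to treat standard culture as a cue to visit. Sample Collection and Preparation says "Urine samples obtained at the first visit are part of routine standard care and thus will be sent to the Clinical Microbiology Lab", and its list of 12-week assays omits standard culture. But the Visit 2 text has urine collected for the same analysis as at visit 1, and the aliquot sent for standard culture and EQUC is not limited to one visit. The cue is uncertain, and the point does not rest on it.

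Nor is the design without any safeguard. Urine from the same visits is also sequenced, each sample at least twice, and the inverse Simpson and Shannon indices come from a software pipeline. A fall in EQUC counts with no 16S counterpart would be noticed. EQUC also uses several media and atmospheres, so a species able to grow on more than one plate would have to be missed on each. These arguments limit the risk to the EQUC count. They do not remove it: Expectations states its numerical prediction in EQUC species, and Possible Limitations treats culture and sequencing as complementary.

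Finally, this is a pilot, and random codes cannot hide arrival dates. Both are true. They bear on priority and on how much the fix achieves, but not on whether the gap exists.

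**Conclusion.** The point holds in a limited form. The plan codes samples by subject, does not mask the EQUC reader to visit, and relies on a manual choice of colonies in a single-group comparison with a predicted direction. Masking is therefore not assured. Whether the reader in fact knows the visit, and whether any bias would follow, cannot be determined from the documents.

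The size is unknown. The 10% to 25% figure rests entirely on an assumed shift of 0.2 to 0.5 species and is an upper bound for that shift. The concern is specific to the EQUC count, and no comparable reader mechanism is identified for the 16S indices or the AMP assays. This is an inexpensive improvement to make before plates are read. It gives no reason to doubt the study as a whole.

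**What to change.** In Sample Collection and Preparation and in the Statistical Analysis Plan, replace the per-subject number on the EQUC research aliquot with a random specimen code that carries no subject, visit or date. State that the reader has no access to earlier results. Clinic staff keep the table linking code to subject and visit until species identifications are locked. The same codes may be used for the 16S and AMP samples for convenience.

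The cost is a relabelling step at the de-identification that staff already perform, a link table, and EQUC accessioned separately from any clinical culture order. The last item means dividing what is now described as one aliquot. Visits, assays and sample size do not change.

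Masking would be partial. Specimens arriving in the first 12 weeks of enrolment must be baseline, and those arriving after the last enrolment must be week 12. If enrolment were even over W weeks and every return visit fell at exactly 12 weeks, the share of specimens arriving while both visits are possible would be (W − 12)/W for W of 12 or more. That is none at W = 12, 12/24 = 50% at W = 24 and 36/48 = 75% at W = 48. The enrolment period is not stated, so these durations are assumptions. The protocol should acknowledge this limit.
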